6.6.1 Lost to Follow Up

A participant will be considered lost to follow-up if he or she repeatedly fails to return for scheduled visits and is unable to be contacted by the study site.

The following actions must be taken if a participant fails to return to the clinic for a required study visit:

- The site must attempt to contact the participant and reschedule the missed visit as soon as possible and counsel the participant on the importance of maintaining the assigned visit schedule and ascertain whether or not the participant wishes to and/or should continue in the study.
- Before a participant is deemed lost to follow up, the investigator or designee must make every effort to regain contact with the participant (where possible, 3 telephone calls and, if necessary, a certified letter to the participant's last known mailing address or local equivalent methods). These contact attempts should be documented in the participant's medical record.
- Should the participant continue to be unreachable, he/she will be considered to have withdrawn from the study.

6.7 Clinical Trial Subject Database (CTSdatabase)

CTSdatabase is a clinical trial subject registry that maintains the privacy and security of research subjects while providing sponsors and investigators with crucial information about subjects' current and/or previous study participation.

CTSdatabase has been shown to reduce the number of duplicate and professional subjects entering clinical trials.

The use of this database must be presented to all subjects participating in this protocol. If subjects refuse to provide authorization, the study team should be notified. At the time of providing the Informed Consent for the study, the Investigator or designee will explain the IRB-approved Subject Database Authorization to the subject and witness the signature.

During screening, site staff that have received training and login information should access www.ctsdatabae.com and enter the last seven digits of the subject study ID and authorized subject identifiers. An immediate report detailing matches is generated and should be printed for source documentation. The report will specify either (1) no matches found, (2) a match was found with a subject participating in another study within 30 days or (3) the subject matches with a subject who has *pre*-screened at another site.

At the last subject contact, CTSdatabase staff will automatically close out subjects (SF, ET or Completer) based on IWRS information.

7 STUDY DRUG MANAGEMENT

7.1 Description of Study Drug

7.1.1 Investigational Product

An investigational product (IP) also known as investigational medicinal product (IMP) in some regions, is defined as follows:

A pharmaceutical form of an active substance or placebo being tested or used as a reference in a clinical study, including products already with a marketing authorization but used or assembled (formulated or packaged) in a way different from the authorized form, or used for an unauthorized indication, or when used to gain further information about the authorized form.

The investigational product should be stored in a secure area according to local regulations. It is the responsibility of the investigator to ensure that investigational product is only dispensed to study subjects. The investigational product must be dispensed only from official study sites by authorized personnel according to local regulations.

In this protocol, IP is zavegepant 10 mg IN and will be provided as single use disposable Aptar UDS devices fully prepared and ready for administration. Zavegepant is packaged as 4 devices per box.

Non-Investigational Product

Other medications used as support or rescue medication for preventative, diagnostic, or therapeutic reasons, as components of the standard of care for a given diagnosis, may be considered as non-investigational products.

In this protocol, non-investigational product(s) is/are: standard of care medications for migraine treatment

7.1.2 Formulation

Zavegepant (BHV-3500), is formulated as 10 mg IN for intranasal single dose administration using an Aptar Unit Dose System (UDS) liquid spray device

7.1.3 Packaging, Shipment and Storage

The product storage manager should ensure that the study drug is stored in accordance with the environmental conditions (temperature, light, and humidity) as determined by the sponsor. Please see the Investigator Brochure for specific conditions. If concerns regarding the quality or

appearance of the study drug arise, do not dispense the study drug and contact the Sponsor/CRO immediately.

7.2 Dose and Administration

7.2.1 Method of Assigning Subject Identification

The Investigator or site designee will need to access an Interactive Web-based Response System (IWRS) in order to register each subject. Initially, after informed consent is obtained at the screening visit, the Investigator or designee will enter the subject into the study and obtain a subject number assignment. At the baseline visit and subsequent visits in the long-term treatment phase, container assignments will be obtained by the Investigator (or designee) via the IWRS system. This subject number must not be reused for any other participant in the study. Subjects will maintain their subject number assigned at screening, throughout the trial.

Subjects may not be rescreened for this study.

Study drug will be assigned via the IWRS system; the system will assign specific container numbers for all study drug to be dispensed to the subject. Sites will be responsible for recording the container numbers dispensed to the subject on the Drug Accountability Form provided in the Regulatory Binder, as well as ensure appropriate documentation of dispensation in the subject's medical record.

Once a subject completes the study, or if a subject is discontinued early from the study, the Investigator or designee must access the IWRS to document discontinuation of the patient from participation in the study.

7.2.2 Selection and Timing of Dose and Administration

Study drug (zavegepant) will be assigned to subjects via the IWRS. There are no dose adjustments in this study. Subjects will receive 4 devices containing zavegepant in a box/container and may receive more than one box of 4 devices at a study visit. Subjects will be dispensed study drug at the baseline visit, after eligibility is confirmed based on the subject's pre-baseline laboratory tests and other screening procedures.

Subjects will be instructed to administer one spray from a single device to treat a migraine. Subjects must be instructed that they cannot administer more than one spray (or device) per calendar day. Subjects will dose for up to 52 weeks. Subjects may administer study drug a maximum of 8 times per month (every 28 days). Subjects who demonstrate poor compliance with study drug instructions or who do not administer study drug may be involuntarily discontinued from the study.

Study drug may be interrupted and re-started after consultation with the Sponsor medical monitor.

7.2.3 Dose Modifications

Not applicable

7.3 Blinding and Unblinding

Not applicable.

7.4 Study and Treatment Compliance

Responsible study personnel will dispense the study drug to the study subjects. Subjects should use all devices in one box/container before starting to use the devices in the next container. Accountability and compliance verification should be documented in the subject's study records.

Subjects must be counseled at all study visits on the importance of taking the study drug as directed. Treatment compliance, through review of study drug doses reported electronically, and review of the returned study drug, should be assessed by site staff at each study visit. Discrepancies between doses reported electronically, review of study drug, and information provided by subject, must be documented in the source record. Incorrect or missing dosing data and migraine data that are reported in the eDiary will be corrected through either a Data Clarification Record or a Medication Reconciliation Form, as appropriate.

Investigators should inform subjects that involuntary termination from the study will occur in cases where non-compliance is identified (defined as both non-compliance with the daily evening report and/or with average number of monthly doses of study drug). Study staff should contact a subject in between the monthly study visits if the subject demonstrates non-compliance the daily evening migraine report and document the contact in the source notes, to identify potential lost to follow up or non-compliant subjects as early as possible.

Investigators must monitor subjects for possible cases of abuse of study drug (patients taking study drug for non-therapeutic purposes, e.g. for psychoactive effects such as high or euphoria). Investigators should assess study drug accountability discrepancies (e.g. missing study drug, loss of drug, or non-compliance cases in which more study drug was used, as compared to expected). Investigators should obtain more information and explanation from patients when there are study drug accountability discrepancies. See Section 8.1.1.

Cases of potential study drug abuse or overdose (including cases of non-compliance with study drug dosing instructions or patients who discontinue treatment without returning study drug) should be documented in the source record and reported as an AE or SAE as appropriate. Dosing

errors (e.g. accidentally administering 2 sprays from 2 devices in one calendar day) should be reported as deviations.

If poor compliance continues, (i.e., non-compliance with study drug dosing instructions or instances of lost study drug during the long-term treatment phase), discontinuation of the subject from the trial will be considered.

In the event a study visit cannot be completed due to the COVID-19 pandemic, the study site may send drug via certified and tracked courier to the subject, if allowable by the policies of the study site. The sponsor should be consulted prior to shipping drug. For WOCPB subjects, a negative pregnancy test must be documented for continued participation in the study and prior to shipping study drug.

7.5 Destruction and Return of Study Drug

All unused and/or partially used study drug can be sent back to the drug depot for destruction only after being inspected and reconciled by the responsible study monitor or the sponsor's designee. If it is site policy to destroy study drug on site, it is the Investigator's responsibility to ensure that arrangements have been made for the disposal, procedures for proper disposal have been established according to the applicable regulations, guidelines and institutional procedures, and appropriate records of the disposal have been documented. The unused study drugs can only be destroyed after being inspected and reconciled by the responsible study monitor or the Sponsor's designee.

8 ADVERSE EVENTS

An Adverse Event (AE) is defined as any new untoward medical occurrence or worsening of a pre-existing medical condition in a subject or clinical investigation subject administered an investigational (medicinal) product and that does not necessarily have a causal relationship with this treatment. An AE can therefore be any unfavorable and unintended sign (including an abnormal laboratory finding for example) symptom, or disease temporally associated with the use of the investigational product, whether or not considered relate to the investigational product.

Adverse events can be spontaneously reported or elicited during an open-ended questioning, examination, or evaluation of a subject. In order to prevent reporting bias, subjects should not be questioned regarding the specific occurrence of one or more AEs.

If a specific diagnosis or syndrome is identified by the Investigator, this should be recorded as the AE, rather than recording (as separate AEs) the individual signs/symptoms or clinically significant laboratory abnormalities known to be associated with, and considered by the Investigator to be a component of, the disease/syndrome.

There are two types of adverse events, Serious Adverse Events (SAE) and Non-Serious Adverse Events (AEs).

8.1 SERIOUS ADVERSE EVENT

8.1.1 Definition of Serious Adverse Event (SAE)

An SAE is any event that meets any of the following criteria at any dose:

- Death
- Life-threatening
- Inpatient hospitalization or prolongation of existing hospitalization
- Persistent or significant disability/incapacity
- Congenital anomaly/birth defect in the offspring of a subject who received study drug
- Other: Important medical events that may not result in death, be life-threatening, or require hospitalization, may be considered an SAE when, based upon appropriate medical judgment, they may jeopardize the subject and may require medical or surgical intervention to prevent one of the outcomes listed in this definition. Examples of such events are (but not limited to):
 - o Intensive treatment in an emergency room or at home for allergic bronchospasm

- o Blood dyscrasias or convulsions that do not result in inpatient hospitalization
- o Development of drug dependency or drug abuse
- o Potential drug induced liver injury (see Section 8.1.6)
- Abuse or Overdose of medication
 - Potential study drug abuse (including cases of excessive non-compliance with study drug dosing instructions or subjects who discontinue treatment without returning study drug) should be documented in the source record and reported as an AE or SAE as appropriate. Investigators must monitor subjects for possible cases of abuse of study drug (subjects taking study drug for non-therapeutic purposes, e.g. for psychoactive effects such as high or euphoria). Investigators should obtain more information and explanation from subjects when there are study drug accountability discrepancies
 - Potential study drug overdose is defined in Section 8.1.4.

Definition of Terms (the below applies to both non-serious adverse events and serious adverse events).

Mild: Is usually transient and may require only minimal treatment or therapeutic intervention. The event does not generally interfere with usual activities of daily living.

Moderate: Is usually alleviated with additional specific therapeutic intervention. The event interferes with usual activities of daily living, causing discomfort but poses no significant or permanent risk of harm to the subject.

Severe: Interrupts usual activities of daily living, significantly affects clinical status, or may require intensive therapeutic intervention.

Life threatening: An AE is life threatening if the subject was at immediate risk of death from the event as it occurred; i.e., it does not include a reaction that if it had occurred in a more serious form might have caused death. For example, drug induced hepatitis that resolved without evidence of hepatic failure would not be considered life threatening even though drug induced hepatitis can be fatal.

Hospitalization: AEs requiring hospitalization should be considered SAEs. Hospitalization for elective surgery or routine clinical procedures that are not the result of AE (e.g., elective surgery for a pre-existing condition that has not worsened) need not be considered AEs or SAEs. If anything untoward is reported during the procedure, that occurrence must be reported as an AE, either 'serious' or 'non-serious' according to the usual criteria.

In general, hospitalization signifies that the subject has been detained (usually involving at least an overnight stay) at the hospital or emergency ward for observation and/or treatment that would not have been appropriate in the physician's office or outpatient setting. When in doubt as to whether 'hospitalization' occurred or was necessary, the AE should be considered serious.

The following hospitalizations are not considered SAEs in Biohaven clinical studies (but may be considered non-serious AEs):

- A visit to the emergency room or other hospital department <24 hours that does not result in an admission (unless considered "important medical event" or event that is life threatening);
- Elective surgery planned prior to signing consent;
- Admissions as per protocol for a planned medical/surgical procedure;
- Routine health assessment requiring admission (i.e., routine colonoscopy);
- Admission encountered for another life circumstance that carries no bearing on health and requires no medical intervention (i.e., lack of housing, care-giver respite, family circumstances).

Disability/incapacitating: An AE is incapacitating or disabling if the experience results in a substantial and/or permanent disruption of the subject's ability to carry out normal life functions.

8.1.2 Assessment for Determining Relationship of AE to Study Drug:

The relatedness of each AE to study drug must be classified based on medical judgement and according to the following categories. The definitions are as follows:

Related: This category applies to AEs that are considered, with a high degree of certainty, to be related to the study drug. An AE may be considered related when it follows a temporal sequence from the administration of study drug, it cannot reasonably be explained by the known characteristics of the subject's clinical state, environment, or toxic factors, or other modes of therapy administered to the subject. An AE may be considered related when it follows a known pattern of response to the study drug, or if the AE reappears upon re-challenge.

Possibly related (non-serious AEs only): This category applies to AEs that are considered to have an unlikely connection to study drug, but a relationship cannot be ruled out with certainty.

Unlikely related (non-serious AEs only): This category applies to AEs that do not follow a reasonable temporal sequence from the administration of the study drug. The AE may readily

have been produced by the subject's clinical state, environmental or toxic factors, or other modes of therapy administered to the subject.

Unrelated: This category applies to AEs that are considered with a high degree of certainty to be due only to extraneous causes (e.g. subject's clinical state, environment, toxic factors, disease under study, etc.) and does not meet the criteria of other categories above.

8.1.3 Collection and Reporting Serious Adverse Events

Following the subject's written consent to participate in the study, all SAEs, whether related or not related to study drug, must be collected, including those thought to be associated with protocol-specific procedures. All SAEs must be collected that occur during the screening period and throughout the course of the study up to and including the 14 days after last dose. The investigator should report any SAE occurring after this time period that is believed to be related to study drug or protocol-specific procedures.

All SAEs should be followed to resolution or stabilization.

An SAE report should be completed for any event where doubt exists regarding its status of seriousness.

If the investigator believes that an SAE is not related to the study drug, but is potentially related to the conditions of the study (such as a withdrawal of previous therapy or a complication related to study procedure), the relationship should be specified in the narrative section of the SAE Report Form.

SAEs, whether related or not related to study drug, overdose (see Section 8.1.4), potential drug induced liver injury (see Section 8.1.6) and pregnancies (see Section 8.1.5) must be reported within 24 hours of the Investigator becoming aware of the event. In this study SAEs are reported in the EDC and on the SAE form.

The Investigator is responsible for reporting all SAEs and all Other Important Medical Events to within 24 hours of learning of the event. Will then immediately notify the Biohaven Medical Monitor of the event. The Investigator is responsible for submitting all applicable events to the Independent Review Board (IRB) as per the IRB's reporting requirements. Additionally, the Investigator, or designated staff, is responsible for entering the SAE information in the Electronic Data Capture (EDC) system (i.e.: event term, start stop dates, causality, intensity).

Any serious adverse event must be reported immediately or no later than 24 hours after awareness of the event to adverse event, using the SAE report form, must be sent to by facsimile (fax), which is the preferred method of submission, within 24 hours after awareness of the event:

• North America - PPD

If a form is unable to be submitted within 24 hours, the SAE may be reported by telephone via the Safety Hotline Number:

North America – PPD

If only limited information is initially available, follow-up reports are required. If an ongoing SAE changes in its intensity or relationship to study drug or if new information becomes available, a follow-up SAE report should be sent within 24 hours of the Investigator becoming aware of the updated information using the same procedure used for the transmission of the initial SAE and the same event term should be used.

The minimum information required for an initial SAE report is:

Sender of report (Site number, Investigator name)

Subject number

Protocol number (BHV3500-202)

SAE term (if an SAE is being reported)

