	The screening phase includes a screening visit and a 28-day Observation Phase. Upon completion of the screening visit, subjects will electronically

[figure not shown]
record migraine occurrence every day. If a migraine occurs, subjects record migraine intensity and whether the migraine was treated. Subjects will report all concomitant medications, including migraine standard of care medications, in a concomitant medication log.

During the 28-day observation phase, the subject will return to the clinic for the pre-baseline visit. At the pre-baseline visit, a blood sample for laboratory tests will be collected.

After the pre-baseline visit, subjects will return to the clinic for the baseline visit. At the baseline visit, eligibility for continued participation in the study will be assessed. After the investigator reviews the results of the pre-baseline laboratory assessments and all other eligibility criteria, eligible subjects may be dispensed study drug and may start dosing in the long-term treatment phase. If eligible for the long-term treatment phase, subjects will be instructed that they can take study drug at the onset of a migraine. Subjects will be instructed that they can treat a maximum of 8 migraines per month (28 days) during the long-term treatment phase and that only one administration of study drug is allowed per calendar day. Subjects are required to continue to electronically record their migraine occurrence and migraine intensity daily. If the subject administers study drug to treat a migraine, the dose of study drug must also be reported on that day. Subjects will continue to record any concomitant medication use (including migraine standard of care medications) in the paper diary throughout the course of the study.

Subjects will have study visits at Week 2, Week 4 and every 4 weeks through Week 52. The Week 52 (+/- 7 days) visit is the end of treatment visit. There is a follow up visit 14 days (+/- 2 days) after the Week 52/end of treatment visit (see Table 1).

STUDY SCHEMATIC

Total study duration approximately 58 weeks

TABLE OF CONTENTS

1 IN	TRODUCTION AND RATIONALE	.14
1.1	THERAPEUTIC AREA BACKGROUND	.14
1.2	PRODUCT DEVELOPMENT BACKGROUND	.15
1.2.1	NON-CLINICAL PHARMACOLOGY	.15
1.2.1.1	NONCLINICAL PHARMACOKINETICS, PHARMACODYNAMICS,	
	AND TOXICOLOGY	.15
1.2.2	CLINICAL EXPERIENCE	.15
1.2.2.1		
1.2.2.2		
1.2.3	OTHER CLINICAL / NON-CLINICAL STUDIES	
1.2.3.1	PHASE 1 STUDIES	.16
1.2.4	CLINICAL ADVERSE EVENT PROFILE	.16
1.2.4.1		

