⁴ Full physical exam at screening and EoT; targeted physical exam guided by signs and symptoms at all other specified visits.

⁵ If the end of treatment physical exam from BHV3500-301 was done within 4 weeks of the screening visit for BHV3500-202, it does not need to be completed at screening. The data from the BHV3500-301 physical exam must be entered in the BHV3500-202 CRF.

⁶ Height collected at screening only.

⁷ Hematology includes hemoglobin, hematocrit, RBCs, WBCs with differential, platelets; Chemistry includes creatine kinase, sodium, potassium, chloride, bicarbonate, calcium; glucose, HbA1c, BUN (urea), serum creatinine, uric acid, LDH, total protein, albumin.

⁸ LFTs includes AST, ALT, Alkaline Phosphatase, and bilirubin (total, direct, indirect)

⁹ Lipid panel includes cholesterol, LDL, HDL, and triglycerides

¹⁰ The BHV3500-301 EoT ECG can be used as the screening ECG for BHV3500-202 if the visits are done on same day.

¹¹ Urinalysis includes pH, specific gravity, ketones, nitrites, urobilinogen, leukocyte esterase, protein, glucose, and blood. If blood, protein or leukocytes are positive, reflex to microscopic examination

Week 2 Follow-up Safety Visit (14 days after EOT visit +/- 2 days) ¹		X (urine) ^{Error!} Bookmark not defined.	×	×				
Weeks 8, 12, 16, 20, 24, 28, 32, 36, 40, 44, 48, 52 (or EoT) (all visits +/- 7 days) ¹		X (urine) ¹³	X	X ¹⁵	X	X (Weeks 12, 24, 36, 52/EoT only)	X (Week 52/EoT)	X (Week 52/EoT)
$\frac{\text{Week}}{4 \text{ (Day}}$ $\frac{29 + -}{2 \text{ days})^{1}}$		X (urine)	×	X	X			
$\frac{\text{Week 2}}{\text{(Day)}}$ $\frac{15}{+/-2 \text{ days)}^{1}}$			×	×	X			
Baseline Visit (Day 1)			×		X			
Visit Up to 5 days prior to Baseline Visit		X (serum)	×	X	X	×		
Observation Phase (28 days +/- 2 days)					X			
Screening Visit	X	X (urine)	×	X				
Procedure	FSH, if applicable, to determine WOCBP status ¹²	Pregnancy Test	AE and SAE assessment ¹⁴	Sheehan Suicidality Tracking Scale	Subject report of migraine occurrence and intensity	Migraine-Specific Quality of Life Questionnaire (MSQ) v 2.1	Preference of Medication	Satisfaction with Medication

¹² If WOCBP status was determined by FSH in BHV3500-301 the subject is considered to have the same status in BHV3500-202

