4.3.6 Follow up Safety Visit

Subjects will return to the study site approximately 14 days after the Week 52/End of Treatment visit for a follow up safety visit and applicable study procedures (Table 1). Subjects will return the concomitant medication log at this visit for one final review by the study site staff. This visit must be conducted in person, but may be delayed if necessary due to local COVID-19 safety requirements).

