8.3.1 Collection and Reporting of Non-Serious Adverse Events

The collection of non-serious AE information should begin at the screening visit through the Follow up Safety Visit. Non-serious AE information is reported from the start of the observation phase to establish a baseline status for a subject.

Non-serious adverse events should be followed until conclusion or stabilization, or reported as SAEs if they become serious. Follow-up is also required for non-serious AEs that cause interruption or discontinuation of study drug or those that are present at the end of study treatment.

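### Protocol 8.1.3 ends mandatory all-causality SAE collection 14 days after the last dose, whereas 8.3.1 and Table 1 run to a follow-up visit timed from the end-of-treatment visit

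*Protocol*

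**What the plan says.** Three parts of the protocol bear on when SAE collection ends.

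- **Section 8.1.3** requires all SAEs, related or not, from consent and "throughout the course of the study up to and including the 14 days after last dose". It continues: "The investigator should report any SAE occurring after this time period that is believed to be related to study drug or protocol-specific procedures". After day 14, the duty to report therefore depends on causality.
- **Section 8.3.1** sets the window for non-serious events: "The collection of non-serious AE information should begin at the screening visit through the Follow up Safety Visit".
- **Table 1 (section 4.3)** has a single row, "AE and SAE assessment", marked at the follow-up visit. Its footnote gives a common start for serious and non-serious events and no separate end for SAEs.

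The follow-up visit is anchored to a visit, not to a dose. The synopsis says: "There is a follow up visit 14 days (+/- 2 days) after the Week 52/end of treatment visit". Section 4.3.6 agrees, and adds: "This visit must be conducted in person, but may be delayed if necessary due to local COVID-19 safety requirements". It gives no upper limit on that delay.

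In SAP 7.2, the on-treatment safety period ends 7 days after the last dose, and the follow-up safety period starts there with no upper limit. SAP 6.4.1.5 tabulates AEs by intensity and SAEs for the same follow-up analysis set. SAP 6.4.7 plans narratives for follow-up SAEs.

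**The concern.** With daily dosing, last dose and EOT would nearly coincide and the two anchors would give the same date. Here the drug is taken only when a migraine occurs, so the anchors separate by however long the subject has gone without a spray. A site applying 8.1.3 literally would have to record a mild, unrelated complaint raised at the follow-up visit, but would not have to report an unrelated hospitalization on the same day.

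What is at stake is late capture of non-fatal SAEs. The SAP's follow-up SAE table would combine all-causality capture up to day 14 after the last dose with related-only capture after it. The companion table of all follow-up AEs would hold non-serious events collected regardless of cause throughout. The causality filter is also coarse. Under 8.1.2 the two intermediate categories apply to non-serious events only, so an SAE is either related, a category meant for events the investigator is highly certain about, or unrelated. In a single-arm, open-label safety study without a data monitoring committee, it is better that late SAE capture does not depend on that judgement or on which section a site happens to follow.

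**Working it through.** The plan gives no figure to reproduce on this point. The check is date arithmetic followed by an illustration.

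**Inputs from the documents**
- All-causality SAE window ends at last dose + 14 days (Protocol 8.1.3).
- Non-serious window ends at the follow-up visit, EOT + 14 days, +/- 2 (Protocol 8.3.1, synopsis, Table 1).
- On-treatment period ends at last dose + 7 days (SAP 7.2).
- At most 8 sprays per 28 days and one per calendar day (Protocol 7.2.2). An average below 2 doses per month over 3 consecutive months leads to discontinuation (Protocol 6.6).

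**Step 1: the gap.** Let g be the days from last spray to the EOT visit.
- SAE window ends at EOT + 14 - g.
- Non-serious window ends at EOT + 14 (+/- 2).
- Shortfall = g (+/- 2) days. Any COVID-19 delay of the follow-up visit adds to it day for day.

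| g (days) | SAE window ends | Shortfall (range) |
|---|---|---|
| 0 | EOT + 14 | 0 (-2 to 2) |
| 3 | EOT + 11 | 3 (1 to 5) |
| 7 | EOT + 7 | 7 (5 to 9) |
| 14 | EOT | 14 (12 to 16) |
| 28 | EOT - 14 | 28 (26 to 30) |

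Once g exceeds 2 days, the SAE window is the shorter one wherever the visit falls within its +/- 2 days.

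**Step 2: effect on the SAP's follow-up period.** That period begins on day 8 after the last dose and, to the nominal visit, lasts (g + 14) - 7 = g + 7 days. Seven of these (days 8 to 14) have all-causality SAE capture; the other g have related-only capture. With g = 7, half of the period is affected (7 of 14 days).

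**Step 3: effect on the primary endpoint.** The on-treatment period closes 14 - 7 = 7 days inside the SAE window for every g, so there is no effect.

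**Step 4: illustration of g.** The documents give no distribution of g. Assume a constant daily dosing probability p = r/28, where r is sprays per 28 days. Then mean g = (1 - p)/p and P(g >= k) = (1 - p)^k.

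| r | Mean g | P(g > 2) = (1 - p)^3 | P(g >= 14): closes on or before EOT | P(g >= 15): closes strictly before EOT |
|---|---|---|---|---|
| 2 | (26/28)/(2/28) = 13.0 | 80% | (26/28)^14 = 35% | 33% |
| 4 | (24/28)/(4/28) = 6.0 | 63% | (24/28)^14 = 12% | 10% |
| 8 | (20/28)/(8/28) = 2.5 | 36% | (20/28)^14 = 0.9% | 0.6% |

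The rates run from the low-use threshold to the permitted maximum. They are assumptions, not observed use.

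**The case against.** The best reply is that 8.1.3 need not be read so strictly. Its sentence covers the whole course of the study, and the follow-up visit belongs to the study. The same section requires all SAEs, related or not, to be reported within 24 hours of awareness and puts no end date on that. Table 1 has sites assess SAEs at the follow-up visit. On this reading the 14 days is a loose description of the post-treatment follow-up, and a site working from Table 1 loses nothing.

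Much of this stands, and it makes the problem one of conflicting passages rather than a settled shorter rule. It does not remove the problem. The next sentence of 8.1.3 treats 14 days after the last dose as the end of a period beyond which only related events are due, so the literal reading is open to any of the roughly 65 sites.

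A reader might also infer more than the documents support:
- **That SAE collection stops altogether.** It does not; related SAEs remain reportable without limit.
- **That the death tables become incomplete.** SAP 6.4.1.1 also identifies deaths from the Study Exit Status CRF, and Protocol 9.3 lists deaths whatever their onset.
- **That the gap is follow-up time with no SAE coverage.** Related events are still due, and Table 1 still schedules the assessment.

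**Conclusion.** The point holds as an inconsistency that affects data capture. Sections 8.1.3, 8.3.1 and Table 1 do not give one end point for SAE collection. On the literal reading of 8.1.3, the all-causality window is shorter than the non-serious one by the time from last spray to EOT (+/- 2 days). That result needs only the documents' own dates. The events exposed are non-fatal SAEs rated unrelated and occurring late; the outputs exposed are the descriptive follow-up SAE table and the related narratives.

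How often this matters cannot be established from the documents. The gaps and percentages in the second table rest on assumed rates and on constant daily dosing, and they fall steeply as use rises. No number of missed SAEs can be estimated. Since the primary endpoint is untouched, this should be corrected but does not threaten the study's main result.

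**What to change.** Reconcile the passages by rewording 8.1.3 so that all SAEs, regardless of causality, are collected from consent through the Follow-up Safety Visit or 14 days after the last dose, whichever is later. Keep the present rule that later SAEs believed related remain reportable.

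The follow-up visit arm brings SAEs into line with 8.3.1 and Table 1. The last-dose arm appears in neither of those; it is kept so that no current coverage is lost, for example when the last spray is on the EOT day and the visit takes place at EOT + 12, or when the visit is missed. With the change, the SAE window is never shorter than the non-serious one, whatever the gap.

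The cost is one sentence in the protocol, a matching line in the SAE reporting instructions given to sites, and slightly more SAE reporting. No visit is added, and the SAP's analysis periods do not change.
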